### **Physical Exam**

A physical exam will include:

- Baseline medical examination and
- Study specific procedures

#### ***Baseline medical examination will include***

- Blood pressure
- Height measurement
- Weight measurement

Blood pressure will be determined in the right arm in the sitting position. Large cuff will be used as necessary. Participants with BP > 140/90 would be referred to the resident Physician for management. Height and weight will be recorded to the nearest 0.1 cm and 0.1 kg respectively. Participants will be weighed while dressed in light

clothing, without shoes. A physical exam with standard pelvic and breast exam will be performed on all patients by a study physician.

***Study specific medical examination will include:***

- Waist and hip circumferences measurement
- Hirsutism assessment
- Acne assessment
- Alopecia assessment
- Acanthosis nigricans assessment

Data Collection:

Types of data:

Independent variables

1. Socio-demographic variables
2. Baseline characteristics

Dependent variables

3. Primary outcome
  - I. Prevalence of PCOS
4. Secondary outcome
  - II. Phenotype of PCOS
  - III. Genotype of PCOS
  - IV. Prevalence of obesity
  - V. Prevalence of hirsutism
  - VI. Prevalence of diabetes

Data collection instrument:

The methods of collecting data for assessment of study objectives include the use of standardized interview-based medical forms; surveys; physical examination.

The CRF developed for this study include; clinical and anthropometric section; radiological report section and laboratory result section. The questionnaire section will seek information on socio-demographic variables, reproductive history with emphasis on menstrual cycle (dating and regularity) and gynecological history, hirsutism, acne, medications, and family history. The anthropometry and clinical section will document the physical findings such as hirsutism, acne, alopecia, acanthosis nigricans, and thyroid enlargement. The pelvic ultrasonographic findings will be recorded in the laboratory result section. Subjects will also complete the

following standardized data instruments or forms as appropriate: FG Score self-assessment, SF-12, Beck depression inventory, Epworth sleepiness scale, and uterine fibroid assessment.

Expected duration of subject participation is approximately from 1 to 3 cycles or 12 weeks. Approximate time to complete enrollment is 9 to 12 months. Approximate time to complete study is 18 to 24 months.

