#### Secondary

2. To determine the distribution of phenotypes among women diagnosed with PCOS in the above objective overall and by ethnicity. PCOS sub phenotypes are as follows: Phenotype A – clinical and/or biochemical hyperandrogenism (HA) and oligi-/anovulation (OA), and polycystic ovarian morphology (PCOM); B – HA and OA; C – HA and PCOM; and D – OA and PCOM;
3. To determine the risks for, metabolic syndrome, depression, obstructive sleep apnea symptoms, fibroids, and general health issues for PCOS women versus women without PCOS in the age groups 18 – 45 years.
4. To determine the genotype of PCOS in Trinidad.

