### **Quality assurance**

1. Instrument validation – A standardized uniform assessment tool (the CFR) was developed for this study. The CFR will be de-identified and pretested.
2. Data collection – the study register will be used to compare participants with non-participants and this will help exclude self-selection bias. The CRF will be used for the collection of data from all the participants. Each study participant will be given a unique identification number to enable follow-up, retrieval of data including missing information and clarification of information. The questionnaire section of the CRF will be completed by a trained researcher to ensure completeness and accuracy of data. The clinical and anthropometric section will be completed by a medically trained researcher. Participants with an initial hirsutism (mFG) score of 3 or more will be re-assessed by a single physician. The pelvic ultrasonography will be performed by experienced Gynecologist trained in pelvic ultrasonography. The antral follicular count (AFC) will be done in the transverse section of the ovary. The blood samples and initial laboratory analysis will be performed by suitably trained research/laboratory assistance. The blood specimens will be collected in the appropriate tubes/containers, and Aprotinin will be added to plain tubes to prevent the breakdown of small proteins that many be useful for measures. The initial blood specimen will be labelled with the participants' unique identification (ID) number, last menstrual period (LMP), date and time of sample collection; while the small aliquots in plastic containers will be labelled with the unique ID number and date. There will also be a laboratory system that records how often the sample has been retrieved, thawed and refrozen. A subject tracking log for longitudinal observational study (Appendix IV) will be used to monitor the data collection process/procedure.
3. Staff training – The members of the research team (PI, Co-investigators and Research Assistants) will undergo a few days training on the various aspects of the study procedure and protocol. The training will cover the following areas: responsible to conduct research, the study protocol, education of

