potential study participants, recruitment of study participants, completion of the consent form and CRF, physical examination and anthropometric measurements, biological sample collection and labelling, pelvic ultrasonography, and laboratory techniques and procedures for biological specimen handling, processing and storage. The degree of intra-observer accuracy and consistency, and inter-observer consistency will be established for key physical measures such as hirsutism score, clinical examination and anthropometric measurement, volume of blood sample measurement and pelvic ultrasonography.

4. External quality assessment laboratory - A reference laboratory will be used for the batched analysis of stored sample for external quality assurance. The laboratory of [name] will serve as the reference laboratory.
5. An external advisory group will be established a prior to:
  - a. Advise on the study design
  - b. Help train local staff in study techniques
  - c. Assist in resolving issues that arise during the study
  - d. Assist in identifying collaborative units and laboratories.

[name] and the other collaborators from USA will form the external advisory group.

6. Data management - The CRF will be used to collect data from each study participant. All CRF will be checked for missing data within 24 hours of completion, and any missing data will be detected and collected immediately. The sociodemographic and baseline characteristics, and the clinical findings and anthropometric measurements will be documented in hard copy (CRF) and then imputed into the appropriate software (such as Microsoft Access and SPSS) at regular intervals. The radiological and laboratory data will be documented in the hard copy CRF of each study participant and subsequently imputed to the software. The study register and the CFRs will be kept confidential to avoid identification of the participants beyond the purposes described above. Data entered into the software will only bear the unique ID number. All data and records will be linked with the participants' unique ID number. The electronic database will be password protected. Quality control staff will perform periodic checks for accuracy of data entry (by comparing the hard copy and the electronic chart) and for data accuracy (by re-interviewing the participants). Statistical analysis will be done using SPSS.

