**Job description**

The physicians and nurses will be responsible for identification of potential study participant, education and counselling, and filling the questionnaires. The medically trained Research Assistants will be responsible for the anthropometric measurements and initial physical examination. The physicians will be responsible for the physical examination. The Gynecologist will be responsible for the pelvic ultrasonography. The Research Technician and Assistant will be responsible for the blood sample collection and processing under the supervision of the pathologist.

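### The pelvic ultrasound shares one case report form with the other diagnostic findings and nothing masks its reader, so polycystic-morphology calls are open to bias

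*Combined protocol and SAP*

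**What the plan says.** **Where results are recorded.** The data collection instrument is one CRF per woman: "The CRF developed for this study include; clinical and anthropometric section; radiological report section and laboratory result section". Its questionnaire section covers "reproductive history with emphasis on menstrual cycle (dating and regularity) and gynecological history, hirsutism, acne, medications, and family history". For the examination, "The anthropometry and clinical section will document the physical findings such as hirsutism, acne, alopecia, acanthosis nigricans, and thyroid enlargement". For the scan, "The pelvic ultrasonographic findings will be recorded in the laboratory result section". Quality assurance, item 6 (data management), repeats the arrangement: "The radiological and laboratory data will be documented in the hard copy CRF of each study participant".

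**Who scans.** Quality assurance, item 2, says "The pelvic ultrasonography will be performed by experienced Gynecologist trained in pelvic ultrasonography" and fixes the plane in which antral follicles are counted. The Job description agrees: "The Gynecologist will be responsible for the pelvic ultrasonography". It gives the physical examination to physicians and medically trained research assistants.

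**What PCOM decides.** The secondary objectives define four phenotypes. A needs hyperandrogenism (HA), oligo-/anovulation (OA) and PCOM. B needs HA and OA. The other two are "C – HA and PCOM; and D – OA and PCOM".

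**What is not stated.** No section masks the ultrasound reader to the clinical, menstrual or hormonal findings. None says who completes the ultrasound entry, or in what order interview, examination and scan take place. The visible text gives no threshold for PCOM. One may be in the diagnostic flow chart (Figure 1), which is not shown.

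**The concern.** PCOM rests on an operator's count, and borderline counts call for judgement. A reader who knows that a woman is hirsute or has irregular cycles may search harder for follicles, or settle a borderline count as positive. Among women with exactly one of HA or OA, such a call turns a non-case into phenotype C or D and enters the primary outcome directly. Among women with both, it moves B to A and alters the phenotype distribution, a secondary objective. The confidence interval for prevalence reflects sampling error only and would not show either effect. Once the scans are done, the readings cannot be masked afterwards.

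**Working it through.** **Step 1: the plan's own precision.** The inputs come from Strategies for Sampling, Recruitment and Retention: Z = 1.96, P = 0.134, D = 0.03.

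n = Z² × P × (1 − P) / D² = 3.8416 × 0.134 × 0.866 / 0.0009 = 495.3

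The stated 495 reproduces, and 495 / 0.50 = 990 gives the number to approach. The ±3 points is thus a sampling margin with no allowance for misclassification.

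**Step 2: who is affected.** From the phenotype definitions, a case has at least two of HA, OA and PCOM.

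| Woman has | Without PCOM | With PCOM | Effect of an extra PCOM call |
|---|---|---|---|
| Neither HA nor OA | not a case | not a case | none on prevalence |
| HA only | not a case | C | adds a case |
| OA only | not a case | D | adds a case |
| HA and OA | B | A | phenotype only |

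**Step 3: size.** Let q be the share of women with exactly one of HA or OA. Let δ be the net rise in the proportion of them called PCOM-positive because the reader knows the other findings. Then:

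shift in prevalence = q × δ

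The documents give neither quantity, so both are assumed and shown as a range. Each cell gives the shift in points, then the resulting prevalence starting from 13.4%.

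| q | δ = 5 points | δ = 10 points | δ = 15 points |
|---|---|---|---|
| 10% | 0.5 (13.9%) | 1.0 (14.4%) | 1.5 (14.9%) |
| 20% | 1.0 (14.4%) | 2.0 (15.4%) | 3.0 (16.4%) |
| 30% | 1.5 (14.9%) | 3.0 (16.4%) | 4.5 (17.9%) |

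The shift reaches the ±3 margin at q = 20% with δ = 15 points, or at q = 30% with δ = 10 points. At q = 10% it would need δ = 0.03 / 0.10 = 30 points. If δ is negative, the same formula lowers prevalence.

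**Step 4: a route the formula leaves out.** The notes to Table 1 obtain a day 22–24 progesterone in women with apparently regular bleeding only if they have hirsutism and/or PCOM. If that rule is followed, a PCOM call can trigger the test that may then reveal OA, so the first row of the Step 2 table is not entirely inert. Study procedure describes the mid-luteal sample without that restriction, so it is unclear whether this route operates.

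**The case against.** The strongest objection is that the CRF text says where results are filed, not what the gynecologist sees. The questionnaire and clinical sections are assigned to named types of staff, but nobody is named for the ultrasound entry. The result could be transcribed later, and the ultrasound page could be separable, since the form itself is not in the documents. Scanning and examination belong to different roles. Hormone samples are batched, and the androgens go to a research laboratory, so those values may not exist in the form at the time of the scan. A reader might infer from the shared form that the scan is read unblinded and that prevalence is therefore inflated. The documents do not support either step. They show access and the absence of any masking rule, not an unmasked reading. Nor do they fix the direction: a reader who knows that cycles are regular could settle a borderline count downward. All of this stands.

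It is also fair that Quality assurance, item 3, commits to establishing intra- and inter-observer consistency for measures that include pelvic ultrasonography, and that item 2 requires an experienced, trained operator. These limit loose reading, but they address reproducibility: two readers who both know the clinical picture can agree and share a bias. Separate roles are not masking either. Nothing keeps the gynecologist from the rest of the form, or from being the study physician who does the pelvic examination.

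Finally, masking can achieve only so much. Visible hair cannot be hidden. If inclusion criterion (b) is applied as written, entry alone tells the reader that the woman has a qualifying feature. This limits the benefit, mainly on the HA side. Menstrual history, recorded scores and any available laboratory values can still be withheld.

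**Conclusion.** The concern holds as a gap in the plan: the scan is recorded in the form that carries the other diagnostic criteria, and masking of its reader is nowhere specified. An upward bias in prevalence is plausible, because the women whose status PCOM decides are those who show one positive criterion. It is not certain, and the documents do not establish it.

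The size rests wholly on assumed values: 0.5 points at the low end (q = 10%, δ = 5 points) and 4.5 points at the high end (q = 30%, δ = 15 points), against ±3 points planned. The low end is minor, while the high end exceeds the whole margin. Because the protection is cheap and cannot be added after data collection, the change is worth making before recruitment.

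**What to change.** - **Separate sheet.** Record the scan on its own form carrying only the unique ID and any information needed for safety, completed without access to the questionnaire, clinical or laboratory sections.
- **Numbers, not a verdict.** Enter follicle count and ovarian size as numbers, and derive PCOM at data entry from the study's pre-stated definition. If that definition is in Figure 1, cite it; if not, state it before the first scan.
- **Merge by ID.** The data management item already links all records by the unique ID, so no new system is needed.
- **Text to amend.** State the masking rule in the data collection instrument section and in Quality assurance, items 2 and 6. Also reconcile the data collection instrument section with itself: it lists a radiological report section but sends the ultrasound findings to the laboratory result section.

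**Cost.** One extra form and a few sentences, with no added visits or tests. The Job description already separates scanning from examination, so no new role is needed, provided the gynecologist who scans a woman has not also examined or interviewed her. The masking is partial for the reasons given under the objection, and the report should say so.

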### **Laboratory methods and Techniques**

Laboratory assay will be conducted under the direct supervision of the investigators in the clinical pathology using facilities at the School of Veterinary Medicine and Department of Pre-clinical Sciences, Faculty of Medical Sciences, The University of the West Indies, Trinidad.

### **Screening (local clinical) Laboratory**

All women will be requested to present fasting for 12 hours at the initial screening visit, and on days 1-10 of their menstrual cycle. Blood work will be sent as described (see Table 1 below) and will be analyzed in the Biochemistry Laboratory at Preclinical Sciences. Research samples will be processed at the sample lab. An aliquot of serum from this visit will be frozen and maintained for subsequent core lab determinations (serum from two 7.5 cc red top tubes at baseline). 1 ml of serum from these visits will be aliquoted into 1.5 cc microfuge tubes and will be stored at –20 to –70 degrees Celsius and batched for periodic shipping to the central core lab facility for eventual assay. The purpose of aliquoting is to preserve basal levels of potential analytes in a frozen state until assay to avoid the deleterious effects of thawing and re-freezing.

**TABLE 1. Screening laboratory evaluations\***

PCOS Inclusion/Exclusion labs	
•	TSH**
•	PRL**
•	17-OHP***
•	P4++
•	oGTT**

\* To be determined in local clinical lab (MDS Biochemistry Laboratory) in UWI, Trinidad.

\*\* All subjects.

\*\*\* For subjects with oligomenorrhea and/or hirsutism and/or PCOM only, who do not use Hormonal Contraception (HC).

++ For subjects with hirsutism and/or PCOM, who have apparently regular menstrual bleeding a day 22–24 progesterone (P4) level will be obtained.

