## Selection criteria

### Inclusion criteria

- a) Female, ages 18 to 45 years., all ethnic backgrounds.
- b) The participants must have at least one of the following two features:
  - i) Dermatological signs or complains of clinical hyperandrogenism such as unwanted facial or body hair, loss of scalp hair (alopecia) or persistence acne (pimple).
  - ii) Signs or complains of ovulatory dysfunction such as irregular menses (oligomenorrhoea, amenorrhea or polymenorrhoea), history of anovulation or ultrasonographic findings of polycystic ovarian morphology.

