### Study procedure

Potential study participants from selected geographical locations will be invited to participate in the study. A confidential study register (see attached) containing details of potential study participants (name, age, height, weight, blood pressure and contact phone number) will be kept. Potential study participants will be counselled on the objectives of the study and the study protocol. If the potential participant refuses to participate, no further contact will be made with the participant. Informed consent (see attached) will be obtained from each eligible study participant before recruitment for the study. A subject tracking log for longitudinal observation study will be used to track eligible subjects.

After an informed consent, data will be collected from each study participant using a standard format in a clinical report form (CRF) for uniform data collection from all participants. Each CRF will contain a unique serial identification number. The CRF will be filled by a suitably trained researcher (including the PI, co-investigators and medically trained research assistants). All CRFs will be checked for missing data within 24 hours of completion, and any missing data will be detected and collected immediately.

Each participant will undergo anthropometric measurements (weight, height, waist, circumference and hip circumference) and physical examination for hirsutism, acne, alopecia, acanthosis nigricans, and thyroid enlargement. Participants with an initial hirsutism (mFG) score of 3 or more ( $\geq 3$ ) will be re-assessed by a physician.

After overnight fasting (of 8 hours or more), 10 ml of venous blood sample will be collected from each study participant; within the first seven days of spontaneous or induced menstrual cycle. About half (5 ml) of the venous blood will be collected in an EDTA-containing tube for plasma/DNA and the remaining in a plain tube for serum. Aprotinin will be added to plain tubes to prevent breakdown of small proteins that may be useful for measures. Aprotinin is a small protein bovine pancreatic trypsin inhibitor that inhibits trypsin and related proteolytic enzymes. During the mid-luteal phase of the menstrual cycle (between day 20 and 24), 5 ml of venous blood sample will be collected in a plain tube for serum progesterone.

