**TABLE 2. Laboratory evaluations and sample storage in research.**

Research lab

• SHBG

• Total and Free Testosterone

• DHEAS

• Blood for DNA extraction for later genetic analysis ☒      Extra blood for repository

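### Study procedure and Table 1 disagree on who has the luteal progesterone test, and Table 1's rule leaves some women with hyperandrogenism untested for anovulation

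*Combined protocol and SAP*

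**What the plan says.** Two places in the combined protocol and SAP describe the luteal progesterone sample.

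- Study procedure: "During the mid-luteal phase of the menstrual cycle (between day 20 and 24), 5 ml of venous blood sample will be collected" for progesterone. The sentence follows the fasting draw taken from every participant and carries no condition on symptoms, ultrasound or bleeding pattern.
- Table 1, Screening laboratory evaluations, footnote: "For subjects with hirsutism and/or PCOM, who have apparently regular menstrual bleeding a day" 22 to 24 progesterone sample is taken. The same table marks TSH, prolactin and the glucose tolerance test as applying to all subjects, but not progesterone.

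The case definition is in the secondary objectives. Hyperandrogenism (HA) is "clinical and/or biochemical hyperandrogenism (HA"), so it is not confined to hirsutism. The remaining phenotypes are "B – HA and OA; C – HA and PCOM; and D – OA and PCOM", where OA is oligo- or anovulation; B needs no PCOM. Inclusion criterion b(i) gives as signs of clinical hyperandrogenism not only unwanted hair but also "loss of scalp hair (alopecia) or persistence acne (pimple"). Criterion b(ii) lists a history of anovulation among the signs of ovulatory dysfunction.

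Table 2 assigns "Total and Free Testosterone" to the research laboratory.

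**The concern.** For a woman who bleeds regularly, the progesterone result is the plan's laboratory evidence on whether she ovulates. It therefore feeds both the primary prevalence and the A–D split in secondary objective 2. Field teams following Study procedure and teams following Table 1 would test different women under one protocol.

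Table 1's entry condition is also narrower than the plan's own definition of HA. A woman with hirsutism or PCOM has her ovulation checked. A woman whose HA takes another form, and who has no PCOM, does not. The OA criterion is then ascertained unequally across the phenotypes that the study intends to compare.

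**Working it through.** **1. The plan's own figure.** Inputs from Strategies for Sampling, Recruitment and Retention: Z = 1.96, P = 13.4%, D = 3 points.

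n = 1.96² × 0.134 × 0.866 / 0.03² = 495.3, which matches the stated 495. At 50% enrolment, 495 / 0.5 = 990 approached, as stated. The conflict does not alter n. It affects how cases are counted within it.

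**2. The two rules side by side**, for a regularly bleeding enrolled woman with no recorded history of anovulation:

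| Features | Study procedure | Table 1 | If progesterone shows anovulation |
|---|---|---|---|
| Hirsutism, no PCOM | sampled | sampled | can be B |
| Any HA with PCOM | sampled | sampled | moves from C to A |
| PCOM, no HA | sampled | sampled | can be D |
| Acne, alopecia or raised androgens; no hirsutism, no PCOM | sampled | not sampled | would be B, but under Table 1 there is no test |

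Only the last row differs. No section makes a raised androgen trigger a progesterone sample. In the text reviewed, no section gives a progesterone threshold for OA or says how a woman without a result is classified. The section on data management and statistical analysis does not mention it.

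**3. Effect on prevalence.** Let f be the share of analysed women in the last row, and a the proportion of them who are anovulatory. Neither is in the documents; both are assumed. Taking 13.4% as the true prevalence:

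- counted as unaffected: P − f·a
- dropped: (P − f·a) / (1 − f)

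| f | a | Women missed, 495·f·a | Counted as unaffected | Dropped |
|---|---|---|---|---|
| 5% | 10% | 2.5 | 12.9% (−0.5) | 13.6% (+0.2) |
| 10% | 5% | 2.5 | 12.9% (−0.5) | 14.3% (+0.9) |
| 10% | 20% | 9.9 | 11.4% (−2.0) | 12.7% (−0.7) |
| 10% | 30% | 14.8 | 10.4% (−3.0) | 11.6% (−1.8) |

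With f from 2% to 20% and a from 5% to 30%, counting these women as unaffected costs 0.1 points (0.02 × 0.05) to 6.0 points (0.20 × 0.30). If they are dropped, the estimate falls only when a exceeds 13.4%; below that it rises.

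**4. Width of a both-ways report.** Counting the group first as ovulatory and then as anovulatory gives P − f·a and P − f·a + f, a gap of exactly f. At f = 5%, a = 10% the range is 12.9% to 17.9%. At f = 10%, a = 20% it is 11.4% to 21.4%. If f is that large, the gap exceeds the planned ±3 points, so settling the rule before sampling is worth more than handling it afterwards.

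**The case against.** The conflict may be milder than it looks. Days 22–24 lie inside days 20–24, so one draw can meet both windows. The Study procedure sentence does not itself repeat that every participant is sampled, and Table 1's footnote could be read as supplying the group. That makes the text ambiguous rather than harmless: nothing says the footnote governs, and if it does, the gap in the last row of the table follows.

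A reader might also infer several stronger claims. The documents do not support them.

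- *Such women can never be phenotype B.* A recorded history of anovulation counts as ovulatory dysfunction in inclusion criterion b(ii), and the classification tree (Figure 1) is not shown. Only the laboratory route is missing.
- *Women with HA and no PCOM go untested.* Hirsute women without PCOM are tested and can reach B. Only non-hirsute HA is left out.
- *Androgen results come too late to prompt a test.* The Screening Laboratory section does freeze and batch serum for later core assay. But Study procedure batches hormone samples regularly so that results are timely and participants can be classified, and it plans a repeat androgen analysis at the end of the study. Participation may run to 12 weeks and three visits. What can be said is that no rule makes a raised androgen a trigger.
- *Prevalence is biased downward.* That requires untested women to be counted as unaffected, which no section states. Nor would it be the net bias: criterion b requires a PCOS-type feature at entry, which pushes the estimate up.

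The biochemical branch is also narrow. A regularly bleeding woman with raised androgens but no skin or hair complaint, PCOM or history of anovulation does not meet criterion b. Acne and alopecia carry most of the argument.

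**Conclusion.** Wrong as written. The two sections conflict on who has the luteal progesterone test and differ on its window. Following Table 1 leaves enrolled, regularly bleeding women with non-hirsute HA and no PCOM without a laboratory test for anovulation, while women with hirsutism or PCOM are tested. Phenotype B is under-ascertained as a result.

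The effect on prevalence is conditional: downward if untested women are counted as unaffected, in either direction if they are dropped. The documents do not allow its size to be derived. The illustration of 0.5 to 2.0 points rests on assuming that 5–10% of the 495 women are in the group and 10–20% of those are anovulatory. It shows that the effect could be appreciable against ±3 points, not that it is. It is the effect of this rule alone.

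**What to change.** **Protocol.** Reconcile Study procedure and Table 1 into one statement of who is sampled and in which window, and repeat it identically in both places. Check that statement against the HA definition in the secondary objectives, so that any group left untested is left out knowingly. Which group and window to use is a clinical decision for the investigators; no choice is proposed here.

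**Analysis.** Where a woman's ovulatory status depends on a progesterone result that she does not have, code it as unknown rather than as ovulatory. Report the number of such women, and give prevalence and the A–D split twice: with them counted as ovulatory and with them counted as anovulatory.

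**Cost.** Protocol wording, one added sensitivity analysis, and at most some luteal samples that Study procedure already describes.
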